6.6.6 Side Effects

Adverse Reactions

In a study of critically ill patients with ARDS, serious adverse events (SAEs) and safety findings were consistent with a critically ill patient population with a wide range of underlying disease processes. More adverse events (AEs) of rash, hypernatremia, dysphagia and pneumonia were reported in patients on APN011 compared with placebo, although many of these events were reported in the follow-up period.

No adverse systemic hemodynamic effects have been observed in patients with pulmonary arterial hypertension (PAH), but clinical experience is limited to single doses.

No evidence of immunogenicity was found in the clinical studies to date, but further studies are needed to provide definitive information.

Further information can be found in the IB, Chapter 5.3 [6].

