8.5.3.2.1 Adverse Events

The AEs will be listed per patient using MedDRA terminology (lower level term, preferred term and system organ class) and will be reported in tables summarizing the frequency of patients with AEs and AEs by treatment and body system, the number of AEs and patients with AEs by treatments and the characteristics of AEs.

For the hematology, clinical laboratory and the urine analysis deviations from the reference ranges will be summarized in frequency tables.

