8.7.1.2.7 Safety Endpoint

The safety evaluations will include analyses of AEs and SAEs, changes in vital signs, clinical laboratory assessments and in ECG parameters. The analysis of safety will be based on the SAF.

AEs

Pre-treatment AEs will be analyzed separately based on all patients included into the trial. AEs will be summarized by system organ class and preferred term according to Medical Dictionary for Regulatory Activities (MedDRA). The number of events, as well as the number and rate of affected subjects will be reported. AEs (system organ class and preferred term) will also be summarized by seriousness, by severity and by relationship to study medication. No statistical testing procedures will be applied to the analysis of AEs.

Individual patient data listings will be provided for all deaths, patients with other SAEs, unexpected adverse drug reactions (as confirmed by the sponsor's drug safety manager), discontinuation of IMP due to AEs, or premature trial termination due to AEs.

Vital signs

For vital signs, body temperature and body weight standard descriptive summary statistics will be calculated at each scheduled time point

Furthermore, standard descriptive summary statistics will be computed for the absolute change from baseline to each scheduled visit up to the last individual time point

Laboratory measurements

Laboratory data will be subjected to both a quantitative analysis (descriptive summary statistics) and qualitative analysis where frequencies of normal, above normal and below normal values will be computed.

The following analyses will be performed:

- Standard descriptive summary statistics will be calculated at each scheduled measuring time point
- Standard descriptive summary statistics will be calculated for the absolute change from baseline to each scheduled visit
- Frequencies of normal, above normal, and below normal values will be computed at each scheduled measuring time point
- Shift tables displaying changes with respect to the normal range between baseline and each scheduled visit will be provided
- A listing of all patients with abnormal (above normal or below normal) values at any time point will be given

Findings from ECG (12-lead)

Frequencies for the respective categories of (ab)normality will be tabulated.

A patient data listing of all clinically significant abnormal ECG values will be provided.

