The important risks such as multi-organ failure, hypersensitivity, adverse hemodynamic effects and cardiovascular effects will be documented as AEs and will be listed and tabulated by system organ class and preferred term (MedDRA) for treatment emergent adverse events. The number of events, as well as the number and rate of affected patients will be reported for each treatment group. Pre-treatment emergent adverse events will be listed only.

Vital signs

Vital signs include Systolic blood pressure, Diastolic blood pressure, Heart rate, Body temperature and Respiratory rate.

Basic statistics will be computed for absolute values and the absolute change from baseline.

Vital signs will be tested before and after each dose (within 30 min before/after IMP administration) and only once at the visits without IMP. Baseline is defined as Screening value. Daily mean values of assessments before/after IMP administration will be used for calculation of absolute change from baseline at visits with IMP administration.

Oxygen saturation (part of vital signs, but measured only once per visit)

Oxygen saturation will be presented using basic statistics of absolute values for all visits and change from baseline for all after baseline visits.

Clinical laboratory assessments

All continuous results of laboratory data will be converted to standard unit before any calculation if needed. Conversion of all lab values will be described in a separate document.

Value evaluation (Normal / Abnormal – CS / Abnormal – Not CS) will be summarized for all laboratory parameters using frequency table additionally.

Absolute values as well as absolute change from baseline for the following laboratory data will be analysed by visit using basic statistics:

- Biochemistry: AST (GOT), ALT (GPT), Alkaline Phosphatase (AP), Total bilirubin, Total protein, Uric acid, Potassium, Sodium, Albumin, Urea Nitrogen (BUN), Creatinine, eGFR

(assessment is calculated according to the formula used in local laboratory: CKD-EPI, Cockcroft-Gault or MDRD)

- Inflammatory indicators: C-reactive protein (CRP), ESR, Procalcitonin
- Myocardial enzymes: Creatine kinase (total), CKMB, LDH, [alpha] - hydroxybutyrate dehydrogenase ([alpha] -HBD), Troponin (cTnl), Blood lactic acid
- Hematology: Red blood cells (RBC), Hematocrit, White blood cells (WBC), Hemoglobin, Platelets
- Coagulation: Prothrombin time (PT), Activated partial thromboplastin time (APTT), D-dimer, FIB

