Page # of #

<Subtitle for description of contents - if applicable>

<Analysis set>

The numbering NNN of the tables/listings/graphs will be stated in the detailed description (Appendix A).

Following footnote will be used for all generated tables, listings, and graphs:

Date: <Actual date(ddmmmyyyy)>

Program: <Name of program>

All tables, listings, and graphs will be generated in A4 paper format.

The statistical evaluation will be performed using SAS version 9.4 or higher.

5 Changes from Protocol

In the following any changes on statistical aspects as described in the protocol are given:

- Wording of WHO's Proposed Core Outcome Measure Set for Clinical Studies of COVID-19 Infection for consistence (secondary endpoint):
 - Protocol: Time to a 2-point decrease in WHO scoring schema
 - SAP: Time to a to a 2-point decrease in WHO's 11-Point Score system
- Covariables used in statistical models and dynamic randomization
 - Protocol: Age as continuous variable
 - SAP: Age as dichotomous variable (<65 years vs. >= 65 years)

6 Signatures

Statistician:	
[name] FGK Clinical Research GmbH [name] [name] Germany	
11 Jan 2021 Date (ddmmmyyyy)	SN [Signature] Signature

Sponsor:	
[name] APEIRON Biologics AG [name]	
11 Jan 2021 Date (ddmmmyyyy)	[Signature] Signature

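### The SAP text omits the protocol's below/normal/above laboratory frequencies and baseline shift tables, uses a clinical-significance table without direction instead, and does not declare the change

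*SAP*

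**What the plan says.** Protocol 8.7.1.2.7, under laboratory measurements, plans five outputs. Two are categorical and tied to the normal range: "Frequencies of normal, above normal, and below normal values will be computed at each scheduled measuring time point" and "Shift tables displaying changes with respect to the normal range between baseline and each scheduled visit will be provided". Protocol 8.5.3.2.1 repeats the first commitment for haematology, clinical laboratory and urine results: "deviations from the reference ranges will be summarized in frequency tables".

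SAP 4.5 gives this categorical summary: the evaluation of each value as Normal, Abnormal-CS or Abnormal-Not CS "will be summarized for all laboratory parameters using frequency table additionally". It then plans the continuous summaries: "Absolute values as well as absolute change from baseline for the following laboratory data will be analysed by visit using basic statistics". Sodium, potassium, creatinine, eGFR, ALT and haematology are in the list that follows. All abnormal evaluations, clinically significant or not, are also listed. The SAP body names shift tables for one assessment only, the physical examination in SAP 4.2.

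SAP section 5 opens with "In the following any changes on statistical aspects as described in the protocol are given" and lists two items: the wording of the WHO scale endpoint, and age as a dichotomous variable. Neither concerns laboratory data. The SAP refers table details to Appendix A, which is not in the available text.

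**The concern.** A table with the categories Normal, Abnormal-CS and Abnormal-Not CS puts high and low values of the same parameter in one cell. It also puts patients who were abnormal at entry in the same cell as patients who became abnormal on treatment. In acutely ill patients with severe COVID-19, many parameters may already be out of range at baseline, so new abnormalities can be hard to see.

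The protocol itself gives reasons to want such counts. Section 6.7 reports a fatal acute renal failure in the earlier ARDS study that was considered related to study drug, and section 8.3.3.3 names a 50% reduction in eGFR among its holding rules. Section 6.6.6 says of that ARDS study: "More adverse events (AEs) of rash, hypernatremia, dysphagia and pneumonia were reported in patients on APN011 compared with placebo". Section 6.7 qualifies this by calling the hypernatraemia mild and in line with sodium levels on placebo, so sodium is an example here and not an established signal.

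Because section 5 is silent, a reader of the final report could not tell whether the two tables were dropped on purpose.

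**Working it through.** The plan states no figure on this point, so the check is a comparison of texts.

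| Laboratory output in Protocol 8.7.1.2.7 | SAP 4.5 (body) |
|---|---|
| Descriptive statistics by time point | Kept, by visit |
| Absolute change from baseline by visit | Kept, by visit |
| Below/normal/above frequencies by time point | Not specified; Normal/Abnormal-CS/Abnormal-Not CS used instead |
| Shift tables against the normal range, baseline to each visit | Not specified |
| Listing of patients with abnormal values | Kept, as a listing of abnormal evaluations |

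Three of five are kept, two are absent from the body, and none of this appears in section 5.

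Can the retained outputs supply the same information?

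1. SAP 4.9 defines basic statistics as mean, standard deviation, minimum, quartiles, median and maximum. A tail of a few percent lies outside the quartiles, the maximum is one patient, and the mean does not count affected patients.
2. A listing shows individual results but gives no rate by arm.
3. Adverse event tables depend on what is reported. Protocol 8.5.2.2.13.1.4 exempts clinically significant laboratory changes specific to COVID-19 from adverse event recording, so this route rests on judgement at about 40 sites.

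Two illustrations show what the missing tables would add. Both use **assumed** counts with 100 patients per arm; no figure in the documents supports them.

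*Direction.* Suppose sodium is high in 8 and low in 2 patients on APN01, and high in 2 and low in 8 on placebo.
- SAP table, abnormal: (8 + 2)/100 = 10% against (2 + 8)/100 = 10%.
- Protocol table, above normal: 8/100 = 8% against 2/100 = 2%.

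*Baseline.* Suppose 80 of 100 patients per arm are abnormal at baseline and stay so. Of the other 20, 25% become abnormal on APN01 and none on placebo.
- New abnormalities: 0.25 × 20 = 5 against 0.
- SAP table, abnormal: (80 + 5)/100 = 85% against 80/100 = 80%.
- Shift table, among those normal at baseline: 5/20 = 25% against 0/20 = 0%.
- Under the SAP 4.9 convention that shift-table percentages use the overall total, the same cell reads 5/100 = 5% against 0%. The counts 5 and 0 are still visible.

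On denominators, SAP 4.9 includes missing values in frequency percentages. Table 1 of the protocol does not require laboratory tests when the Day 28 visit is by phone. Unless this rule is changed for these tables, missing results would dilute the rates at late visits.

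**The case against.** A reader might infer that the SAP keeps only the site's judgement of significance, that direction and change from baseline are lost, and that hypernatraemia could no longer be seen. The documents do not support this.

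- The clinical-significance table is described as additional. Values and change from baseline are summarised by visit, with sodium named. Signed changes, minima and maxima show direction at group level.
- Abnormal sodium results are listed, and hypernatraemia recorded as an adverse event is tabulated by preferred term and arm.
- Protocol 8.5.2.2.6 has laboratories supply reference ranges and the physician grade out-of-range values. On that reading Normal against Abnormal is largely range-based and only the significance split is judgement. Adding the two abnormal categories would give an out-of-range frequency, though without direction or baseline.
- SAP 4.9 sets a convention for shift tables, and Appendix A is unseen. Laboratory shift tables could be specified there. The convention does not prove it, because physical examinations also use shift tables.
- The first illustration is built so that the totals cancel, and the second assumes that no baseline abnormality resolves. They show what is possible, not what is likely.
- Both missing outputs are descriptive and untested, and could be produced after database lock from the same data.

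All of this stands. It limits the point but does not remove it: none of the retained outputs counts, by arm, the patients who are high, low or newly out of range, and the protocol promised those counts.

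**Conclusion.** The point holds for the SAP body. Two of the five laboratory outputs in Protocol 8.7.1.2.7 are not specified in SAP 4.5, the substitute table carries neither direction nor baseline status, and section 5 does not declare the departure. What is missing is limited to patient-level counts by arm of high and low values and of shifts from baseline. The size of any effect on the safety conclusions cannot be derived from the documents.

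The conclusion rests on one condition: that Appendix A does not already contain the tables. If it does, only a cross-reference is missing. This is a worthwhile, low-cost improvement to safety reporting. It does not touch the primary endpoint, the sample size or any test.

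**What to change.** In SAP 4.5, restore both protocol tables for every laboratory parameter with a reference range, by arm:

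- below/normal/above frequencies at each scheduled visit;
- shift tables against the normal range from baseline to each scheduled visit.

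Base percentages on patients with a value at that visit (for shifts, also at baseline), and state this as an exception to the conventions in SAP 4.9. Keep the clinical-significance table as an extra. If Appendix A already specifies these tables, cross-reference it in 4.5. If the sponsor prefers to leave them out, section 5 should say so and give the reason; that would settle the inconsistency but not supply the counts.

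A shift table from baseline to worst value would be a useful option, but goes beyond the protocol.

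The cost is a short SAP amendment and a little table programming. No new data collection is planned for this, since laboratories already supply the reference ranges under Protocol 8.5.2.2.6.

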6.7 Risk-Benefit Considerations

Based on available information and the design of the clinical trial, the Sponsor considers the trial to be ethically acceptable.

In general, the adverse events in the first in human (FIH) Study (APN01-1-01) occurred with similar frequency between active and placebo treated subjects, without apparent dose-relatedness. In the Phase I-Study 204987 (Effects on the Response to Acute Hypoxia and Exercise) of APN01 with healthy subjects there were no serious adverse events, deaths or other significant adverse events. In the Phase Ib Study 204696 in patients with PAH, there were no SAEs associated with the infusion of GSK2586881 (APN01) or reported within the 2-week period of study observation [6].

In the ongoing open-labeled Phase II a-206246-Study with Patients with PAH there were no SAEs and no anti-ACE2 binding antibodies detected.

The hypernatremia reported with GSK258688 (APN01) in the Phase IIa-ACE114622-Study with patients with acute respiratory distress syndrome was mild and consistent with sodium levels in the placebo group, and a number of events occurred after discontinuation of drug. The episodes of pneumonia in subjects receiving GSK2586881 (APN01) in the same study were all considered nosocomial in origin and occurred between 5-36 days after the last dose of study drug.

During Part A of the Phase IIa-ACE114622-Study 3 subjects experienced a total of 9 SAEs that resulted in death, only one of which (acute renal failure), was considered to be related to study drug, and was reported 4 days after the last dose of study drug.

None of the fatal events in during Part B (3 fatal AEs - 2 in the placebo group due to multiple organ failure and septic shock and one in GSK2586881 (APN01) 0.4 mg/kg BID) was considered to be related to study treatment by the reporting investigator.

In general, the safety findings were consistent with a critically ill patient population with a wide range of underlying disease processes.

Fei Zhou et al. reported age, comorbidities, lymphocytopenia and elevated alanine aminotransferase, d-dimer, creatine kinase, high-sensitivity cardiac troponin I, prothrombin time, and disease severity to be associated with intensive care unit admission. In addition, angiotensin converting enzyme 2, the receptor for SARS-CoV-2, is expressed on myocytes and vascular endothelial cells, so there is at least theoretical potential possibility of direct cardiac involvement by the virus [7].

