8.3.3.3 Criteria for Termination of the Clinical Trial (Holding Rules)

The trial will be supervised by an independent Data Safety Monitoring Board (DSMB). All final decisions, however, regarding study termination or modification will be decided by the Sponsor and in agreement with the independent DSMB.

The clinical trial will be terminated if

- The DSMB requests termination of the clinical trial based on review of all clinical and laboratory data
- The Sponsor, Regulatory Agency or an EC requests the termination of the clinical trial
- 50% reduction in eGFR is observed. In addition, assessment of this parameter will be performed at the DSMB.

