A change in the value of a safety laboratory investigation can represent an AE if the change is clinically relevant or if, during treatment with the IMP, a shift of a parameter is observed from a normal value to an abnormal value, or a further worsening of an already abnormal value. When evaluating such changes, the extent of deviation from the reference range, the duration until return to the reference range, either while continuing treatment or after the end of treatment with the IMP, and the range of variation of the respective parameter within its reference range, must be taken into consideration.

If, at the end of the treatment phase, there are abnormal laboratory values which were not present at baseline, further clinical or laboratory investigations should be performed until the values return to within reference range or until a plausible explanation (e.g., concomitant disease) is found for the pathological laboratory values.

Changes in laboratory values that are clinically significant (cs) and are specific for COVID-19 do not need to be documented as adverse events (AE). Clinically significant changes in laboratory values that are not due to COVID-19 need to be documented as AEs.

The physician should decide, based on the above criteria and the clinical condition of a patient, whether a change in a laboratory parameter is clinically significant and therefore represents an AE.

8.5.2.2.13.1.5 Overdose and Medication Error

Overdose, or medication error (as defined below) must be reported to the Sponsor according to the SAE reporting procedure whether or not they result in an AE/SAE.

Overdose - Intentional or unintentional administration of a dose of study medication higher than the protocol prescribed dose for each patient.

Medication Error - A mistake made in administration, and/or use of the study medication. For studies, medication errors are reportable only as defined below.

Administration of an expired product should be considered as a reportable medication error when associated with an AE, or if otherwise appropriate.

Cases of patients missing doses of study medication are not considered reportable as medication errors.

8.5.2.2.13.2 Serious Adverse Event (SAE) Procedures

8.5.2.2.13.2.1 Reporting Procedures

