4.5 Safety Analysis

Adverse events (AEs) and serious adverse events (SAEs)

AEs will be coded by using the Medical dictionary for regulatory activities (MedDRA) version 23.0.

A treatment emergent adverse event (TEAE) is defined as an AE with AE onset date \geq date of first study medication. If a date is unknown or incomplete and the AE cannot definitely be considered as started before date of first study medication, the AE will be considered as TEAE, unless the AE resolution date is before the date of first study medication.

An AE overview table will be prepared showing the number of patients with at least 1 AE and at least 1 TEAE, TEAEs related to IMP, TEAEs related to IMP procedure (infusion), serious TEAEs, serious TEAEs related to IMP and serious TEAEs related to IMP procedure (infusion) as well as the total number of events in each category.

TEAEs as well as serious TEAEs will be tabulated by system organ class and preferred term (MedDRA). The number of events, as well as the number and rate of affected patients will be reported for each treatment group. Additional tables will be provided for TEAEs (system organ class and preferred term) summarized by severity, by relationship to IMP and by relationship to IMP procedure (infusion).

AEs that occur with AE onset date < date of first study medication are defined as “pre-treatment” events. All AEs for patients without treatment will be considered as pre-treatment AEs. Pre-treatment AEs will be listed only.

Individual patient data listings will be provided for all SAEs as well as additionally for all deaths only (AEs with outcome ‘Fatal’), unexpected adverse drug reactions as confirmed by the sponsor’s drug safety manager (AEs of patients with primary reason for discontinuation ‘Occurrence of a severe adverse reaction (SAR)’), discontinuation of IMP due to AEs (AEs with action taken regarding IMP ‘Drug interrupted’ or ‘Drug withdrawn’), or premature trial termination due to AEs (AEs of patients with primary reason for discontinuation ‘Adverse events necessitating withdrawal from the clinical trial’).

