- Urinalysis: pH, Microscopic examination Red blood cells (BLD), Microscopic examination White blood cells (LEU)
- Stool routine and occult blood: Red blood cells (RBC), White blood cells (LEU)

Frequencies will be provided for the following categorical laboratory results by visit:

- Urinalysis: Glucose, Protein, Red blood cells (BLD), White blood cells (LEU)
- Stool routine and occult blood: Red blood cells (RBC), White blood cells (LEU), Occult blood

All abnormal evaluations (CS as well as not CS) for all laboratory assessments collected in eCRF will be listed.

ECG parameters

ECG evaluation (Normal / Abnormal – CS / Abnormal – Not CS) will be summarized using frequency table.

All clinically significant abnormal ECG values inclusive all ECG parameters (Heart rate [bpm], RR interval [ms], PR interval [ms], QT interval [ms], QRS complex [ms]) will be listed as well.

Detection of viral nucleic acid or viral gene sequencing

Detection of viral nucleic acid or viral gene sequencing data will be presented using frequency tables and listing.

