4.9 Miscellaneous

For qualitative variables the frequencies (absolute and relative) are calculated. If no further remark is given in the description of the tables, following format will be used for all tables with qualitative variables (Note: In shift tables the percentages are based on the overall Total and not on the column Totals):

	Y-variable(s) (e.g., treatment group)					
	Category 1		Category 2		Total	
X-variable(s)	N	%	N	%	N	%
Category 1	xx	xx.x	xx	xx.x	xx	xx.x
Category 2	xx	xx.x	xx	xx.x	xx	xx.x
Missing	xx	xx.x	xx	xx.x	xx	xx.x
Total	xx	100.0	xx	100.0	xx	100.0

For this standard format the description of the tables in Appendix A determines only the X- and Y-variables. If another format of table is described in the details to the tables, the real design will be determined by the technical possibilities within SAS and may not look identical to the provided example. However, all information as displayed will be included.

Quantitative parameters will be described by declaring the mean value, standard deviation, minimum, first quartile, median, third quartile, and maximum. In the description of the tables this will be denoted by „basic statistics“. In general, minimum and maximum will be presented to the same level of precision as the raw data; means and medians, standard deviation, and quartiles will be presented to one further decimal place. P-values will be reported to four decimal places (i.e., 0.xxxx).

For frequency tables, all missing values (including user-defined missing values) will be combined in one category “missing” and included in the calculation of percentages. Percentages will be presented to one decimal place.

Tables and graphics will be presented only for scheduled visits.

The listings are always sorted by treatment group, center, and patient. If a different sorting order should be used for some listings this will be remarked separately. The variables for the special listings are explicitly given in the description of listings. All listings will be presented for the safety analysis set, if not stated differently, and indicator variables for further analysis sets, e.g., full analysis set, will be added if needed.

Enrolled but not treated patients (e.g. withdrawal before treatment) will be considered in tables and listings describing disposition of subjects, analysis sets as well as listings of PDs.

The following title will be used for all generated tables, listings, and graphs:

3570: APN01-01-COVID19 – final analysis

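### SAP 4.5 plans no count by arm of patients whose eGFR fell by 50% or more, although the protocol names that fall as a termination criterion

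*SAP*

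**What the plan says.** Protocol 8.3.3.3 lists the conditions under which the trial will be terminated. The last is "50% reduction in eGFR is observed. In addition, assessment of this parameter will be performed at the DSMB". eGFR is the only laboratory measure named there. The rule does not say whether it applies to one patient or a group, which baseline it uses, or whether a second sample is needed. Protocol 6.7 gives the background: in Part A of the earlier Phase IIa ARDS study, three patients had nine fatal SAEs, "only one of which (acute renal failure), was considered to be related to study drug".

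In SAP 4.5, eGFR is one entry in the biochemistry list under this instruction: "Absolute values as well as absolute change from baseline for the following laboratory data will be analysed by visit using basic statistics". SAP 4.9 defines basic statistics: "Quantitative parameters will be described by declaring the mean value, standard deviation, minimum, first quartile, median, third quartile, and maximum". SAP 4.5 plans three further outputs that bear on renal safety:

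- the site's evaluation (normal, abnormal and clinically significant, abnormal and not) "will be summarized for all laboratory parameters using frequency table additionally";
- a listing: "All abnormal evaluations (CS as well as not CS) for all laboratory assessments collected in eCRF will be listed";
- tables of treatment-emergent and serious treatment-emergent AEs by system organ class and preferred term.

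SAP 4.7 plans no imputation. SAP section 4 keeps unscheduled visits out of tables, apart from doses and assessments relabelled as Screening or Day 8. Footnote 17 to protocol Table 1 lets Day 28 laboratory tests be skipped at a phone visit.

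Protocol 8.7.1.2.7 promises laboratory shift tables from baseline to each visit. SAP 4.5 has none, and SAP section 5 declares only two changes (WHO score wording and the coding of age).

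**The concern.** The protocol states its renal criterion as a relative fall, which is most naturally judged patient by patient. The final analysis describes eGFR by arm and visit, on the absolute scale. A reader of the planned tables could not say how many patients in each arm met the protocol's own threshold.

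Renal injury is likely to affect a minority, so a summary centred on the whole arm is a weak way to show it. The patients who matter most are also the likeliest to be missing from a table by visit, because they died, left early or had their lowest value on an unscheduled sample. At stake is a clear account, by arm, of the one laboratory criterion that the protocol ties to stopping the trial. The primary efficacy analysis is not affected.

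**Working it through.** **Inputs.** From the documents: the 50% threshold (protocol 8.3.3.3), 100 patients per arm (protocol 8.7.2), and seven scheduled post-baseline laboratory visits (protocol Table 1: Days 2, 3, 5, 7, 10, 14 and 28). The documents give no eGFR mean, SD or event rate, so those below are assumptions. The plan has no renal figure to reproduce. Its only calculated figure, 93 per group for 50% v 30%, does reproduce (power 0.800) but has no bearing here.

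**1. Scale.** Relative fall = absolute fall / baseline. A fall of 20 is 20/40 = 50%, 20/80 = 25% or 20/120 = 17%. A table of absolute change therefore cannot be turned into a count of 50% falls.

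**2. Dilution of the mean.** If a share f loses exactly 50% and the rest do not change, mean change = −f × 0.5 × baseline.

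| Baseline | f = 5% | f = 10% |
|---|---|---|
| 60 | −1.5 | −3.0 |
| 80 | −2.0 | −4.0 |
| 100 | −2.5 | −5.0 |

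Now take baseline 80 (SD 25), a 60% fall in affected patients, change of 0 (SD 12) in the others, and 10% v 2% affected. Mean difference = −(0.10 − 0.02) × 0.6 × 80 = −3.84. The SD of change in the 10% arm is √(0.10 × 0.36 × (80² + 25²) + 0.90 × 12² − 4.8²) = √359.5 = 19.0.

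**3. Missing values.** If half of the affected have no value at that visit, the arm means are −(0.05 × 48)/0.95 = −2.53 and −(0.01 × 48)/0.99 = −0.48, a difference of about −2.0. If all are missing, the difference is 0.

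**4. Minimum and quartiles.** In simulation of the 10% arm, the minimum averages about −71 and the first quartile about −11, against about −30 and −8 when no affected patient has a value. The minimum does reveal an extreme case. It does not reveal how many: an arm with only 2% affected still contains at least one with probability 1 − 0.98^100 = 87%, so both arms would usually show an extreme minimum.

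**5. What the count would show.** At 10% v 2%, the risk difference is 8 points. Its standard error is √(0.10 × 0.90/100 + 0.02 × 0.98/100) = 0.033, so the simple 95% CI is about 1.5 to 14.5 points.

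**6. Limits of the count (illustration only).** If affected status were known without error, 15% v 5% gives z = (0.10 − 1.96 × √(2 × 0.10 × 0.90/100)) / √((0.15 × 0.85 + 0.05 × 0.95)/100) = 0.40, or about 66% power. Measured eGFR does worse. Take the worst of seven visits, with noise only in unaffected patients and an assumed within-patient correlation of 0.5. The count then detects 15% v 5% in about 42% of trials (noise SD 15) or 28% (SD 20), against 37% and 28% for mean change. Apparent 50% falls in the 5% arm rise to 12–20%. With a single visit the count does better, 51–61% v 29–38%. No laboratory test is planned, so these figures describe visibility, not lost formal power.

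**The case against.** The best defence is that the SAP reports far more than a mean. The minimum shows the largest fall at each visit. Every abnormal evaluation is listed, clinical-significance frequencies cover all laboratory measures, creatinine and urea nitrogen are summarised, and renal events can enter the AE tables. Multi-organ failure is also among the named important risks. A reader might infer that severe renal loss would vanish from the safety output, but the documents do not support that. A severe case could surface in several places.

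None of these outputs gives the count. The significance table follows site judgement: falls from 130 to 62 (52%) and from 70 to 62 (11%) could get the same label. The SAP does not say that the listing will derive a percentage fall. Protocol 8.5.2.2.13.1.4 lets laboratory changes judged specific to COVID-19 go unrecorded as AEs, even when clinically significant, and renal failure is not among the important risks that the SAP names.

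Second, Appendix A and the separate DSMB SAP were not supplied, and either might contain the table. So the claim is limited to the supplied text. A reader might also infer that the final analysis could never produce the number, or that nobody monitors eGFR. Neither follows: patient-level data would allow the count, and the protocol assigns eGFR to the DSMB. But the DSMB SAP serves monitoring, and the supplied SAP is the one for the final analysis.

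Third, a reader might expect the count to be a far more powerful comparison. Step 6 shows that this depends on measurement noise, and the advantage can disappear with a worst-of-seven-visits definition. That objection stands, and the case does not rest on power.

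Fourth, a count of observed values also misses patients who die or start dialysis before a qualifying sample. That too stands, and the fix has to show them separately.

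**Conclusion.** The point holds in a limited form. The supplied SAP text has no count by arm of patients whose eGFR fell by 50% or more, although the protocol names a 50% reduction as a termination criterion. The planned tables by visit cannot be converted to that criterion, dilute an effect in a minority, and leave out unscheduled samples and patients with no value that day. The other safety outputs narrow the gap without closing it.

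For size, 5–10% of an arm losing half its eGFR moves the mean by only 1.5 to 5 for baselines of 60 to 100, and missing values shrink a difference further. These figures rest on assumed baselines, spreads and event shares. The scale argument and the absence of the count do not.

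Separately, the protocol's laboratory shift tables are missing from SAP 4.5, and section 5 does not declare it. Restoring them would not supply the 50% count, because they track movement across the normal range.

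This is a worthwhile addition to a descriptive safety section. It is not a flaw in the primary analysis.

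**What to change.** Add to SAP 4.5:

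- **Table.** n (%) of SAF patients per arm with any post-dose eGFR at least 50% below baseline, including unscheduled and early-termination samples, with risk difference and 95% CI. Keep it descriptive, without a test. State the denominator and the number with no post-dose eGFR.
- **Beside it.** The number per arm whose fall is confirmed by a second sample, to limit false positives from single readings. Also the numbers who died, or had recorded renal replacement therapy, without a qualifying sample.
- **Listing.** Baseline, lowest value, day and outcome for each patient counted.
- **Shift tables.** Restore the laboratory shift tables of protocol 8.7.1.2.7, or declare their removal in SAP section 5.

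If Appendix A already contains the count, a cross-reference in 4.5 is enough. The sponsor should also reconcile the wording of protocol 8.3.3.3 with the unit and baseline used in this table; no clinical rule is proposed here.

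The cost is one table and one listing from data already collected, plus the shift tables if restored. The downside is that some apparent 50% falls will reflect measurement variation, which is why the confirmed count should stand beside the main one.
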